Laxatives are the main line of maintenance therapy of overflow retentive stool incontinence (ORSI) with satisfying results (**Yik 2012**) stimulant laxatives like senna based laxatives (SBL) are our standard choice in Egypt due to its availability (**Bassiuony 2015**).

Massage is the manipulation of muscles and connective tissues (CT) (superficial and deeper layers) by using different techniques. It has been practiced in many ancient civilizations for thousands of years. (**Weerapong 2005**)

Abdominal massage is a noninvasive, effective, and safe form of constipation management in the general population. (**Lamas et al. 2009, Lamas et al., 2012 and Turan&Asti 2016**) .It provides a low burden of risk, reduces symptoms of chronic constipation, improves the quality of life, decreases the use of laxatives and increases the frequency and consistency of bowel movements (**Smith and Moss, 2008; Moss et al., 2007; Richards 1998; Lamas et al., 2010**).

Subjects and methods:

This randomized controlled study was conducted in the out-patient clinic in the Faculty of Medicine, South Valley University from March 2016 to March 2019. The parents of each child submitted Informed consent. The procedures that followed had No: P.T. REC/012/002277 that approved by the Institutional Ethical Committee Clearance of the Faculty of Physical Therapy at Cairo University. The study had registration number NCT registered on Clinicaltrial.gov.

A total of one hundred and seventy children with overflow retentive stool incontinence were evaluated for eligibility. Twenty-seven children did not complete the treatment course, fifty-eight child excluded due to unresponsiveness or non-compliance to our protocol, and eighty-six child was divided randomly into two groups.

The children were selected according to these criteria: (i) Children's aged ranged from four to fourteen years, (ii) children were from both sexes, (iii) children had a history of overflow retentive stool incontinence. Other children were excluded from our study as they met one of the following criteria: (i) children had suspicion of Hirschsprung's disease, (ii) children had anorectal malformation, (iii) children had organic obstruction, (iv) children failed to complete treatment (if cramping abdominal pain or vomiting occurred), (v) children required bowel surgery.

Group A: Senna based laxative

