The statistical analysis was conducted by using statistical SPSS Package program version 25 for Windows (SPSS, Inc., Chicago, IL). Data were normally distributed by using the Shapiro-Wilk test (parametric data). Additionally, testing for the homogeneity of variance revealed that there was no significant difference ($P>0.05$). Quantitative descriptive statistics included the mean and standard deviation for demographic data (age, weight, height, and BMI), constipation starting dose, constipation end dose, and time till not soiling variables. Qualitative descriptive statistics included number (percentage) for gender, area, breastfeeding, previous incomplete therapy for constipation, full urinary continence, fissure, psychosocial problems, developmental delay, and history of delayed passage of meconium variables. Using paired t-test to compare between rural area and the urban area within massage group and without massage group for constipation starting dose, constipation end dose, and time till not soiling variables. Using independent t-test to compare between massage group and without massage group for demographic data (age, weight, height, and BMI), constipation starting dose, constipation end dose, and time till not soiling variables. Also, to compare between two groups (massage group and without massage group) within the rural area and urban area for constipation starting dose, constipation end dose, and time till not soiling variables. Chi-square test used to compare between massage group and without the massage group for qualitative variables. All statistical analyses were significant at the level of probability ($P \leq 0.05$).

References:

Rasquin A1, Di Lorenzo C, Forbes D, Guiraldes E, Hyams JS, Staiano A, Walker LS. Gastroenterology. 2006 Apr;130(5):1527-37.

Mugie, S. M., Benninga, M. A., & Di Lorenzo, C. (2011). Epidemiology of constipation in children and adults: A systematic review. Best Practice & Research. Clinical Gastroenterology, 25, 3-18.

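### Stopping treatment because of cramping or vomiting is an exclusion criterion and no harm variable is analysed, so the arms cannot be compared on tolerability

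*Combined protocol and SAP*

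**What the plan says.** Under Subjects and methods, the exclusion list opens with "Other children were excluded from our study as they met one of the following criteria". Items (i), (ii), (iii) and (v) are diagnoses, suspected diagnoses or a need for bowel surgery. Item (iv) is different in kind: "children failed to complete treatment (if cramping abdominal pain or vomiting occurred".

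The same section gives the participant flow in this order: "A total of one hundred and seventy children with overflow retentive stool incontinence were evaluated for eligibility"; then "Twenty-seven children did not complete the treatment course"; then "fifty-eight child excluded due to unresponsiveness or non-compliance to our protocol"; and finally "eighty-six child was divided randomly into two groups". Neither group of losses is split by arm, and no reasons are given for the 27.

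The Statistical analysis section names the outcomes compared between arms: "constipation starting dose, constipation end dose, and time till not soiling variables". The remaining variables are demographic (age, weight, height, BMI) or qualitative items such as gender, area, breastfeeding, fissure and developmental delay. Cramping, vomiting, adverse events and withdrawal for harm do not appear. The treatment description requires the starting and ending doses and the time to no soiling to be documented. It mentions no recording of harm at the weekly or monthly visits.

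**The concern.** Criterion (iv) is a consequence of treatment written as an eligibility rule. Applied as worded, it takes out of the study the children whose symptoms stopped their treatment, and no listed variable records what happened to them.

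Both arms take senna, which is increased until soiling stops, and one arm adds abdominal massage three times a day. If massage lowers the dose needed, fewer stops for cramping or vomiting would be a real benefit. If pressure on the abdomen causes pain, that would be a real cost. The planned tables can show neither.

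This differs from the question of which children enter the efficacy comparison. Restoring every child to the dose and time analyses would still produce no harm result, because no harm variable is planned.

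**Working it through.** The plan states no harm rate, sample-size calculation or power, so there is no figure of its own to reproduce. The check has four steps.

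**1. When criterion (iv) can be known.** Treatment lasts 6 months. Failure to complete it because of a symptom can be observed only after it starts, so (iv) cannot be applied at screening. The flow text nevertheless mentions the 27 non-completers before it describes randomisation of the 86.

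- If the losses came before allocation, the 86 had been selected for tolerating treatment, and the 27 have no arm to report.
- If they came after allocation, children were removed from the arms because of a harm.

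On either reading, harms that stopped treatment are absent from the analysed set.

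**2. Flow.** 27 + 58 + 86 = 171, against 170 evaluated: an excess of 1.

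**3. Scale of what cannot be seen.** Assumption: all 27 started treatment. The share who stopped for cramping or vomiting is not given, so one third and all are shown as illustrations. The other non-completers stay in the denominator because, under the same assumption, they also started.

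| Denominator | One third of the 27 (9) | All 27 |
|---|---|---|
| 86 + 27 = 113 | 9/113 = 8.0% | 27/113 = 23.9% |
| 86 + 27 + 58 = 171 | 9/171 = 5.3% | 27/171 = 15.8% |

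The second row adds the 58 children excluded for unresponsiveness or non-compliance, at least some of whom presumably had treatment.

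**4. What the counts allow between arms.** Further assumptions, none stated in the plan: all 27 losses followed allocation, and the 113 starters were split 57 and 56. The table shows non-completion for any reason, with the smaller count placed in the arm of 57; the p-value range covers both placements (two-sided Fisher exact test).

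| Split of the 27 | Proportions | p |
|---|---|---|
| 13 v 14 | 13/57 = 22.8% v 14/56 = 25.0% | 0.83 to 1.0 |
| 9 v 18 | 9/57 = 15.8% v 18/56 = 32.1% | 0.049 to 0.077 |
| 5 v 22 | 5/57 = 8.8% v 22/56 = 39.3% | 0.0001 to 0.0003 |

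The reported counts fit anything from no difference to a large one. They are not evidence of a difference.

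**The case against.** The strongest reply is that the documents place randomisation after the losses. The Abstract also describes 86 children as enrolled and then assigned. Read literally, the 27 were never allocated and say nothing about a difference between arms. This stands as a limit: the 27 cannot be assumed to have an arm, and step 4 is conditional on their having one. It does not rescue the plan, because no harm variable is listed for the 86 either.

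Four stronger readings are tempting, and the documents do not support them.

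- *The analysed children show almost no harm by construction.* Criterion (iv) covers children who failed to complete treatment. A child who cramped and finished can remain, so milder harm is unrecorded but not removed.
- *Zero stops in 86 children implies a low harm rate.* The plan makes no such inference, and it calls the 86 randomised without saying that all completed.
- *23.9% is the maximum stop rate.* It leaves the 58 out of the denominator. If some non-compliance was due to symptoms, 27 is not the largest possible numerator either.
- *The trial claims that massage is safe.* The sentence "Abdominal massage is a noninvasive, effective, and safe form of constipation management in the general population" is cited background in the Introduction. The Abstract's conclusion concerns effect only.

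It could also be said that fissure is analysed and that an initial cleanout not tolerated is mentioned. Fissure is listed among background items with no time point, and the cleanout text names no specific harm and makes it no outcome.

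Finally, the wording of (iv) may double as a rule for stopping treatment. That is a clinical matter, and it is not questioned here.

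**Conclusion.** The point holds for harms that stopped treatment. A stated rule removes the affected children from the study, and no harm variable is planned, so tolerability cannot be compared between arms. This is more than a missing detail, and it does not depend on whether the losses came before or after allocation.

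The size is unknown. The illustrative range of 8.0% to 23.9% rests on all 27 having started treatment and on 113 starters; with the 58 included it is 5.3% to 15.8%. None of these is an estimate or a bound. The flow excess of 1 and the order of randomisation and losses must be reconciled before any rate is reported. The documents do not show that either arm was better or worse tolerated.

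**What to change.** 1. Stop using cramping or vomiting after treatment start as a reason to remove a child from the study population. Leave any clinical rule on stopping treatment as it is; the change concerns only who is counted.
2. For all randomised children, tabulate by arm (a) any recorded cramping abdominal pain or vomiting and (b) stopping treatment for either. Give an exact confidence interval for the difference in stopping proportions, and the senna dose and week at onset where recorded. Label the arms by treatment, because the Abstract and the methods use the letters A and B in opposite ways.
3. State for each of the 27 whether the loss came before or after allocation, the reason, and the arm if allocated. Reconcile 171 with 170.
4. If this information was not recorded, state that the trial gives no evidence on tolerability.

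The cost is one table and a corrected flow account, if the records exist. The study period ended in March 2019 and the treatment description requires only doses and time to no soiling to be documented, so they may not. The counts will be small, the interval wide, and the harm picture less favourable.

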Official Title of Study: -

**MASSAGE WITH SENNA-BASED LAXATIVES VERSUS
SENNA-BASED LAXATIVES IN MANAGING OVERFLOW
RETENTIVE STOOL INCONTINENCE IN PEDIATRICS: A
Randomized Controlled Trial**

Document Date: - 02/12/2020.

**Human Subjects protection review board approval
date: - 03/31/2019**

MASSAGE WITH SENNA-BASED LAXATIVES VERSUS SENNA-BASED LAXATIVES IN MANAGING OVERFLOW RETENTIVE STOOL INCONTINENCE IN PEDIATRICS: A Randomized Controlled Trial

[name]

Assistant Lecturer of pediatric surgery, faculty of medicine, *South Valley University, Qena, Egypt*

[name].

Lecture of physical therapy. Department of Physical Therapy for Pediatrics, Faculty of Physical Therapy, South Valley University, Qena, Egypt

Abstract

Background: Overflow retentive stool incontinence is a common disorder affecting children that affect the quality of life in the form of shame, humiliation, depression, and decrease reduced self-esteem of children. **Aim:** To compare the effect of massage with senna-based laxatives versus senna-based laxatives in managing overflow retentive stool incontinence in pediatrics. **Methods:** Eighty-six children with overflow retentive stool incontinence enrolled in this study and were assessed for eligibility. Children's age ranged from four and fourteen. They were assigned randomly into two groups. Group (A) received abdominal massage with senna-based laxatives and group (B) received senna-based laxatives only. The application of massage was applied for 15 minutes, three times/day for six successive months. **Results:** Post-treatment there was a significant improvement in both groups in favor of massage group, $P < 0.05$. **Conclusion:** Abdominal massage with senna-based laxatives has a great effect on children with overflow retentive stool incontinence than senna-based laxatives only. **Keywords:** Overflow retentive stool incontinence, senna-based laxatives, and abdominal massage.

Introduction

Constipation is the most common colonic motility disorder in children affecting between 0.7% to 29.6 % of the pediatric population (**Rasquin 2006, Mugie 2011**) and is frequently associated with fecal incontinence secondary to overflow (**Voskuijl 2004**)

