Initial cleanout protocol for dis-impaction of the colon with the administration of one or two enemas per day with 20 ccs/Kg warm tap water with a salt enema (0.9 % saline can be made by adding 1.5 teaspoons of salt to 960 ml of water) (**Levitt 2010**) till been clean by radiologically. If initial dis-impaction was failed or not tolerated, shift to dis-impaction under general anesthesia.

Single 10 mg dose senna was given with the start of impaction. After dis-impaction; senna dose was increased if needed by 10 mg/clinic visit/week till achieving no soiling; Documentation of both initial effective starting dose and the time slipped till no soiling. Follow-up visits every month unless soiling recurs if soiling happens; additional dose (by 10 mg) was done. Treatment was continued for 6 months.

At the end of 6 months, the effective ending dose (maintenance dose) was documented.

Group B: Senna based laxative with massage

Laxative treatment as group A in addition to massage technique.

The massage technique was based upon the Tactile Stimulation Method of Birkestad that primarily consists of palm-to-skin stroking, gentle pressure and static touch (**Birkestad 1999**).

The patients lying in a comfortable relaxed supine position and physiotherapist performed slow circular clockwise movements on the abdomen, throw tangential pushing, with digital pulp, slow and gradual pressure, with fingers inclination 45

degrees (**Harrington & Haskvitz 2006**). The pressure applied to the abdomen on each point for 1 min, beginning with the ascending colon, transverse colon, descending colon and sigmoid; this sequence was repeated approximately 15 min. The therapist teaches the parents this technique and asked them to apply at home 3 times/day for 15 min.

Statistical analysis

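### Senna is titrated to response with no ceiling and no definition of non-response, and an unknown number of children left for unresponsiveness; depending on when they left, either the conclusion or the comparison is conditional on response

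*Combined protocol and SAP*

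**What the plan says.** **Dosing** (Subjects and methods, under the senna heading; the massage arm has the same laxative treatment). Senna starts at 10 mg. After dis-impaction, "senna dose was increased if needed by 10 mg/clinic visit/week till achieving no soiling". On relapse, "if soiling happens; additional dose (by 10 mg) was done". Treatment lasts 6 months. The section calls for "Documentation of both initial effective starting dose and the time slipped till no soiling", and for the effective ending (maintenance) dose at 6 months.

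**Exclusions and flow** (Subjects and methods). The text starts from 170 children evaluated. On randomisation it says "eighty-six child was divided randomly into two groups". It gives 27 as the number who did not finish treatment, and reports a further loss as "fifty-eight child excluded due to unresponsiveness or non-compliance to our protocol". One listed exclusion criterion concerns tolerance: "children failed to complete treatment (if cramping abdominal pain or vomiting occurred"). Non-response is not among the listed criteria. The abstract describes the flow differently: "Eighty-six children with overflow retentive stool incontinence enrolled in this study and were assessed for eligibility".

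**Analysis** (Statistical analysis). Starting dose, end dose and time to no soiling are compared between arms by independent t-test at the 0.05 level. The section reports that a Shapiro-Wilk test supported normality and that variances were homogeneous. It gives no analysis population, censoring rule, missing-data rule or proportion soil-free.

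**The concern.** When a drug is titrated to response, the protocol has to say what happens to a child who does not respond. This one does not. A child who tolerates senna but keeps soiling meets no stated stopping point. The cramping and vomiting criterion covers intolerance, and general anaesthesia is the fallback for failed dis-impaction, not for failed senna.

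The gap carries into the analysis. Effective starting dose and time to no soiling do not exist for a child who never becomes soil-free. A dose at 6 months can be recorded for a child still soiling, but not as an effective one. The plan neither counts such children as failures nor says how they enter the t-tests, and some children were excluded for unresponsiveness.

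What is at stake depends on timing:

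- **All left before randomisation:** the comparison among the 86 is not affected by their removal, but the result describes children selected by an unstated rule, while the abstract concludes for children with the condition in general.
- **Some left after randomisation:** the arms are compared conditional on response, and randomisation no longer protects that comparison.
- **Some non-responders remain among the 86:** two of the three outcomes have no value for them.

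There is also a safety aspect: escalation in children aged 4 to 14 has no pre-set end.

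**Working it through.** **1. Flow.** Inputs from Subjects and methods: 170 evaluated, 27 not completing, 58 excluded, 86 randomised.

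- 27 + 58 + 86 = 171, one more than the stated 170. This is a minor discrepancy, but it suggests the three groups are meant to be separate.
- 58/170 = 34.1%; (27 + 58)/170 = 50%.
- The 58 pool two reasons, so the number unresponsive is between 0 and 58.

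**2. When did they leave?**

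- *Before randomisation:* only the 86 are said to be randomly divided, and the 27 and the 58 are counted apart from them.
- *After randomisation:* unresponsiveness and failure to complete are normally seen only under treatment, treatment is described only under the two group headings, and no run-in is mentioned.
- The abstract does not help, since it has 86 assessed for eligibility where the main text has 170.

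The first reading is the more literal. Neither is excluded.

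**3. What the dose rule permits.** Dose after w weekly increases = 10 + 10w mg. An increase at every weekly visit gives 10 + 10 × 12 = 130 mg at week 12 and 10 + 10 × 25 = 260 mg at week 25. This shows only that the rule has no upper limit.

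**4. Illustration, only if children were removed after randomisation.** Assumptions: 43 analysed per arm (arm sizes are not given), normal outcome, no true treatment effect, two-sided t-test at 0.05, and the six worst-outcome children removed in total. The figure is the share of simulated trials in which the t-test significantly favours the more-depleted arm; the nominal value is 2.5%.

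| Split of the 6 removed | Favours the more-depleted arm |
|---|---|
| 6 and 0 | about 22% |
| 5 and 1 | about 13% |
| 4 and 2 | about 7% |
| 3 and 3 | about 4% (each arm) |

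The direction follows whichever arm lost more, so the bias could favour massage or senna alone. With an equal split the average difference is zero.

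**5. The same branch, as proportions.** If all 43 + 43 analysed children were soil-free and m unresponsive children had been removed from one arm only, Fisher's exact test of 43/43 against 43/(43 + m) gives P = 0.058 for m = 5 and P = 0.028 for m = 6 (43/49 = 88%). A difference in response of that size would not appear in the planned analysis, which has no responder proportion.

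**The case against.** The strongest reply is that the 58 were never randomised. Only the 86 are described as randomly divided, and on that reading steps 4 and 5 do not apply. This largely stands. It is the more literal reading, and a reader who infers that randomised children were removed because of their outcome, or that the reported advantage for massage is an artefact of this, goes beyond the documents. What remains on that reading is a limit on generalisability, which is real but has no computable size.

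Second, the illustration is sensitive to the split. The 22% needs all six removals in one arm and exactly the six worst outcomes. Nothing in the documents supports such a split, and with more even splits the inflation is much smaller. This stands too, which is why the whole gradient is shown.

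Third, the t-test may be adequate. If unresponsive children were excluded and every one of the 86 became soil-free, all times are fully observed, and the plan reports checks of normality and equal variance. This stands: the t-test on time is then not itself an error. The objection to it holds only if some analysed or removed randomised child never became soil-free.

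Fourth, a reader might infer from the dose arithmetic that very high doses were given. The documents do not support that. Increases were made if needed, at clinic visits, and children failing treatment through cramping or vomiting were excluded. The point is a missing limit.

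Last, the trial ran from March 2016 to March 2019, so past titration cannot be changed. That is correct and limits the fix. It does not remove the need to say who the 58 were.

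**Conclusion.** The concern holds in a conditional form. It is certain that the plan sets no titration ceiling, does not define non-response, excludes children under that label, and has no responder proportion and no rule for children who never become soil-free. The consequence is not certain. On the more literal reading, the conclusion applies only to children who passed an unstated response filter. If any of the 58 or the 27 had been randomised, the comparison is conditioned on response or completion and may be biased either way.

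The bias cannot be calculated, because the number unresponsive (0 to 58), their arm and their timing are not given. The simulated rates show only that a handful of unevenly distributed removals would matter; they do not estimate what happened. Confidence is medium, because timing decides which consequence applies. The sponsor should act on this, since either branch needs a correction.

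**What to change.** **For the 2016–2019 data**

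- Report the 58 and the 27 by reason (unresponsive, non-compliant, other), timing (before or after randomisation) and arm, as far as records allow.
- If any were randomised, keep them in the analysis. Compare the proportion soil-free by arm, analyse time to no soiling as censored (log-rank or Cox), and compare dose by a rank test with non-responders ranked worst.
- If none were randomised, state the rule that removed them and limit the conclusion to children who passed it.
- State whether all 86 became soil-free. If they did, the t-test on time may stay.

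**For any repeat or continuation**

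- Set one clinician-chosen titration ceiling (a dose or a visit), the same in both arms. Reaching it while still soiling defines non-response, which is then an outcome and not a reason for exclusion.

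**Cost.** A flow table, an analysis rule and one protocol sentence. The dose outcome becomes less granular, and its estimand moves to all randomised children. The re-analysis depends on records of removed children, which the documents do not show were kept.

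### A paired t-test is named for rural versus urban children, who are different, unmatched children; run as written, six p-values would depend on row order and lose power

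*Combined protocol and SAP*

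**What the plan says.** All of the analysis plan is in the Statistical analysis section of the combined document. For area of residence it specifies "Using paired t-test to compare between rural area and the urban area within massage group and without massage group", applied "for constipation starting dose, constipation end dose, and time till not soiling variables". That is 3 outcomes in each of 2 arms, so 3 × 2 = 6 tests.

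The same section treats area as a characteristic of the child, reported as a count and percentage alongside gender: "Qualitative descriptive statistics included number (percentage) for gender, area, breastfeeding".

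For the randomised comparison it uses a different test: "Using independent t-test to compare between massage group and without massage group for demographic data", a sentence that goes on to the three outcomes. It then extends the comparison to each area: "Also, to compare between two groups (massage group and without massage group) within the rural area and urban area".

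The Subjects and methods section selects children on age, sex, history and a list of exclusions, and states that "eighty-six child was divided randomly into two groups". It mentions no matching. No endpoint is labelled primary or secondary.

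**The concern.** A paired t-test analyses differences within pairs. It needs a reason why a given rural value belongs with a given urban value: the same child measured twice, or two children matched in advance. Neither is described here. The pairing would come from the order of rows in the data file.

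Three consequences follow if the test is run as written:

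- Re-sorting the file changes the p-value although no observation has changed.
- When an arm has unequal numbers of rural and urban children, the surplus cannot be paired and is left out.
- Degrees of freedom fall to the number of pairs minus one, so intervals widen and power drops.

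Any statement about rural versus urban children within an arm would then be neither reproducible nor based on all the data. The massage effect itself is not at stake, because that comparison has the right kind of test.

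**Working it through.** **Is there any basis for pairs?** Area is one category per child, no child is described as measured in both areas, and the selection criteria contain no matching. Rural versus urban within an arm therefore has the same structure as massage versus no massage within an area: different children in each group. The plan gives the second an independent test and the first a paired one.

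**Is there a figure to reproduce?** No. The documents state no power, p-value or count for this comparison.

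**Inputs.** From the documents: 86 children in two groups and a significance level of 0.05. Assumed: 43 per arm (86/2), two-sided tests, normal outcomes with equal SD, a true rural–urban difference of d = 0.8 SD, and a range of rural/urban splits.

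**Formulas.** With n₁ rural and n₂ urban children and m = min(n₁, n₂) arbitrary, uncorrelated pairs:

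- Independent (pooled): df = n₁ + n₂ − 2; noncentrality = d / √(1/n₁ + 1/n₂).
- Paired: df = m − 1; noncentrality = d / √(2/m).
- Power is exact from the noncentral t. The 95% CI half-width in SD units is the critical t times the square-root term.

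**Worked case, 30/13.**

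- Independent: df = 41, √(1/30 + 1/13) = 0.332, noncentrality 0.8/0.332 = 2.41, power 65.3%, half-width 2.020 × 0.332 = 0.671.
- Paired: m = 13, df = 12, √(2/13) = 0.392, noncentrality 0.8/0.392 = 2.04, power 46.7%, half-width 2.179 × 0.392 = 0.855.
- Children dropped: 43 − 26 = 17. Interval ratio: 0.855/0.671 = 1.27.

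| Split | Dropped | Power, independent | Power, paired | Half-width, independent | Half-width, paired | CI wider by |
|---|---|---|---|---|---|---|
| 22/21 | 1 | 72.6% | 69.4% | 0.616 | 0.644 | 4% |
| 25/18 | 7 | 71.5% | 61.9% | 0.624 | 0.703 | 13% |
| 30/13 | 17 | 65.3% | 46.7% | 0.671 | 0.855 | 27% |
| 35/8 | 27 | 51.3% | 28.3% | 0.791 | 1.182 | 49% |

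**Sensitivity to d (independent to paired).** At 0.5 SD: 36% to 34% at 22/21 and 24% to 14% at 35/8. At 1.0 SD: 89% to 87% and 70% to 41%.

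**Dependence on row order.** One simulated data set per split was scaled so that the independent p-value was 0.030, and its rows were put in 10,000 random orders.

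| Split | Middle 95% of paired p-values | Orderings with p ≤ 0.05 |
|---|---|---|
| 22/21 | 0.007–0.091 | 69% |
| 25/18 | 0.005–0.19 | 49% |
| 30/13 | 0.003–0.41 | 35% |
| 35/8 | 0.005–0.59 | 24% |

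These shares vary with the simulated data set, most at uneven splits: a second data set at 35/8 gave 38%. Over 20,000 simulated trials per split at 0.8 SD, the paired and independent tests reached different verdicts in 8%, 16%, 25% and 31% of runs.

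**Type I error.** With haphazard row order the paired test rejected a true null in 5.0% to 5.3% of runs. As an extreme bound, sorting both columns by the outcome itself gave 61% with 21 pairs and 53% with 13. The documents say nothing about file order.

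**The case against.** The strongest reply is that this may be only a wording slip. The section uses the independent t-test correctly for every other comparison of means between different children, and the sentence in question concerns comparisons inside each arm, so the writer may have used the word loosely for within-group. In that case no p-value is wrong. The documents cannot settle this. It stands as a reason to ask first which test was run, but the text would still misstate the method.

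Second, rural versus urban is not the randomised comparison, the documents report no result for it, and type I error is not generally inflated. All of that stands, and it limits how much weight the point carries.

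Third, the size of the harm rests on assumptions. At a near-even split the power loss is about 3 points (72.6 − 69.4 = 3.2), and the losses of 19 to 23 points need splits such as 30/13 or 35/8. The row-order ranges use data sets placed close to the 0.05 threshold, where verdicts flip most easily. These are illustrations, not estimates for this trial. The dependence on row order, however, is present at every split.

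Fourth, simply substituting the independent t-test already named in the plan would be enough, given that the section reports no significant difference in variances. That is fair: Welch and the interaction model are preferences beyond the minimum correction.

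**Conclusion.** The concern holds. As written, the plan applies a paired test to unmatched children in six comparisons. This is a stated rule that does not fit the data structure, not a missing detail. If it was followed, each of the six p-values is one arbitrary draw from many that the same data could give. The loss of power at 0.8 SD ranges from about 3 points at 22/21 to 23 points at 35/8 (51.3 − 28.3), on the assumption of 43 children per arm. The actual loss cannot be stated without the rural and urban counts. The conclusion about massage does not depend on these tests. It should be fixed, but it does not threaten the main comparison.

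A separate, smaller point concerns the Results sentence of the abstract: "Post-treatment there was a significant improvement in both groups in favor of massage group". None of the listed tests compares before with after within an arm, so nothing in the plan supports the within-group part. A paired start-to-end dose test would not fill the gap if the analysed starting dose is the one described under the senna-only group: "Documentation of both initial effective starting dose and the time slipped till no soiling". That dose is recorded when soiling has stopped, so the change would describe dosing after response. The identification of the two starting doses is likely but not stated outright.

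**What to change.** 1. Replace the paired t-test for rural versus urban children with an independent-samples t-test, preferably Welch. Alternatively, fit one linear model per outcome with arm, area and the arm-by-area interaction, which also covers the comparison of arms within each area.
2. State which test was actually run. If paired, re-run the six tests; if independent, correct the wording.
3. Report the number of rural and urban children in each arm.
4. Separately, delete the abstract's claim of improvement within both groups and report the between-arm difference with its 95% CI. Do not present a start-to-end dose change within an arm as evidence for massage.

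The cost is one sentence in the Statistical analysis section, a sentence in the abstract and at most six re-run tests, with no new data. Welch gives up a little power against the pooled test when the split is very uneven (46% against 51% at 35/8, 0.8 SD), but stays well above the paired test at 28%. At 22/21, 25/18 and 30/13 its power is 72%, 71% and 64%, within about 2 points of the pooled test.
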